### 3.2 Key Definitions

The following definitions will be used:

- Baseline: The baseline value is defined as the last available valid (quantifiable continuous or categorical value), non-missing observation for each participant prior to first study drug administration. Repeat and unscheduled assessments will be included in the derivation of the baseline values. [REDACTED]
- For FE Segment ([REDACTED]) the baseline value is defined as the last available valid (quantifiable continuous or categorical value), non-missing observation for each participant prior to the study drug administration in each period. Repeat and unscheduled assessments will be included in the derivation of the baseline values. Below table provide the baseline measurement to be considered for each parameter.

Measurement	Period 1	Period 2
Laboratory(Hematology, Chemistry & Urinalysis), Vital Signs and ECG	Pre-dose value captured at Visit 2 Day 1, if missing then value captured at Screening.	Pre-dose value captured at Visit 4 Day 1.

- Change from Baseline: The change from baseline value is defined as the difference between the result collected/derived at a post-baseline visit/time point and the baseline value.

The change from baseline value at each post-baseline visit/time point will be calculated for all continuous parameters using the following formula:

$$\text{Change from Baseline Value} = \text{Result at Visit/Time Point} - \text{Baseline Value}$$

The change from baseline value will only be calculated if the specific post-baseline visit/time point result and the baseline value for the parameter are both available and will be treated as missing otherwise.

- Percent Change from Baseline

Percent Change from Baseline at each post-baseline visit/time point will be calculated for all continuous parameters using following formula.

$$\% \text{ Change from Baseline} = 100 \times [(\text{Post-Dose Visit Value} - \text{Baseline}) / \text{Baseline}]$$

- Study Day: The study day of an event is defined as the relative day of the event starting with the date of the first study drug administration (reference date) as Day 1 (there will be no Day 0).

The study day of events occurring before the first study drug administration will be calculated as:

$$\text{Study Day} = (\text{Date of Event} - \text{Date of First Study Drug Administration})$$

For events occurring on or after Day 1, study day will be calculated as:

$$\text{Study Day} = (\text{Date of Event} - \text{Date of First Study Drug Administration}) + 1$$

Study days will only be calculated for events with complete dates and will be undefined for events that are 'Ongoing' at the end of the study.

Relative days compared to an alternative reference point will be calculated similarly, but the alternative starting reference start date will be used instead of the date of the first study drug dosing.

- Period Study Day: For FE segment, the Period Study Day of an event is defined as the relative day of the event relative to the previous study drug administration date.

$$\text{Period Study Day} = (\text{Date of Event} - \text{Date of Previous Study Drug Administration}) + 1$$

If an event occurs prior to the first administration of study drug, period study day will be calculated as:

$$\text{Study Day} = (\text{Date of Event} - \text{Date of First Study Drug Administration})$$

- Actual Time from First Dose (hours) = (Date/Time of PK Sample collection) – (Date/Time of First Dose on Day 1)
- For FE segment the actual time from first dose (hours) will be derived based on the dosing day in each period.

ie; Actual Time from First Dose (hours) = (Date/Time of PK Sample collection) – (Date/Time of First Dose on Day 1 in each period)

- Actual Time Deviation (hours) = (Actual PK Sample Collection Time Post Dose) – (Scheduled PK Sample Collection Time Post Dose).
- Prior Medications: Prior medications are defined as any medication where the use was stopped prior to the first administration of the study medication.
- Concomitant Medications: Concomitant medications are defined as any medication (other than the study drug) that was used at least once after the first administration of the study drug. Medications that were stopped on the same date as the first study drug administration will be included as concomitant medications. If a clear determination cannot be made (partial medication end dates) the medication will be classified as concomitant.
- For FE segment concomitant medication will be defined as follows:
  - All medications stopped post study drug administration in Period 1 but prior to study drug administration in Period 2 will be attributed to Period 1 treatment only.
  - All medications started prior to study drug administration in Period 1 and stopped after study drug administration in Period 2 will be attributed to both treatments.
  - All medications started post to study drug administration in Period 2 will be attributed to Period 2 treatment only.
- Treatment Emergent Adverse Events (TEAEs) are defined as adverse events that occurred following the first administration of study medication.
- For FE segment treatment emergent adverse events will be defined as follows:
  - TEAEs that start on or after the study drug administration of Period 2 will be attributed to Period 2 treatment only.
  - TEAEs that start on or after the study drug administration of Period 1 but prior to study drug administration of Period 2 will be attributed to Period 1 treatment only.

Any change in severity will be seen as a new event and will be allocated to the treatment in the same way.

If only the event start year (and month) is present, the event will be allocated to all treatment with the same start year (and month), unless the event end date clearly indicates that an event did not occur within certain periods.

If complete dates are missing (start and end dates), the event will automatically be classified as an event for all treatment (Period).

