11.1. Adverse Events

11.1.1. Definition of an Adverse Event

An AE is defined as any untoward medical occurrence in a subject administered a pharmaceutical product and which does not necessarily have a causal relationship with this treatment. An AE can therefore be any unfavorable or unintended sign (including a clinically significant abnormal laboratory finding), symptom, or disease temporally associated with the use of a medicinal (investigational) product.

Medical conditions present at baseline that worsen in severity or frequency after exposure to study drug are considered treatment-emergent AEs (TEAEs). Planned hospital admissions or surgical procedures for an illness or a disease that existed before administration of study drug, and for which the condition has not worsened since starting study drug, are not to be considered TEAEs/treatment-emergent SAEs. Events with emergency room visits that are less than 24 hours will also not be considered SAEs unless they meet one of the criteria listed in [Section 11.2.1](#).

Clinically significant abnormal laboratory tests, 12-lead ECG assessments, or vital sign results may, in the opinion of the Investigator, constitute an AE. However, whenever possible, the underlying diagnosis should be listed in lieu of associated abnormal results. Abnormalities deemed not clinically significant by the Investigator should not be reported as AEs.

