11.1.4.1. Special Instructions for Recording Adverse Events in the eCRF

Diagnosis versus Signs and Symptoms

If a diagnosis is known at the time of reporting, this should be recorded in the eCRF rather than the individual signs and symptoms (eg, record only hepatitis rather than elevated transaminases, bilirubin, and jaundice). However, if a constellation of signs and/or symptoms cannot be medically characterized as a single diagnosis or syndrome at the time of reporting, each individual event should be recorded as an SAE or AE on the eCRF. If a diagnosis is subsequently established, it should be reported as follow-up and should replace the individual signs and/or symptoms as the event term on the eCRF, unless the signs/symptoms are clinically significant.

Adverse Events Occurring Secondary to Other Events

In general, AEs occurring secondary to other events (eg, clinical sequelae or a cascade of events) should be identified by their primary cause. For example, if severe vomiting is known to result in dehydration, it is sufficient to record only vomiting as an SAE or AE on the eCRF. However, medically significant AEs occurring secondary to an initiating event that are separated in time should be recorded as independent events on the eCRF. For example, if severe vomiting leads to acute renal failure, both events should be recorded on the eCRF.

Persistent or Recurrent Adverse Events

A persistent AE is one that extends continuously, without resolution, between subject evaluation timepoints. Such events should only be recorded once on the eCRF. If a persistent AE becomes more severe or lessens in severity, it should be recorded as a new AE on the eCRF.

A recurrent AE is one that occurs and resolves between subject evaluation timepoints, and subsequently recurs. Each reoccurrence of an AE should be recorded on the eCRF.

Abnormal Laboratory Values or Vital Signs

Protocol defined laboratory values and vital signs will be reported as AEs if the abnormal laboratory or vital sign result:

- Requires an adjustment in the study drug(s) or discontinuation of treatment;
- Requires additional testing, excluding repeat testing of the lab in question, or surgical intervention;
- Is associated with accompanying signs/symptoms that are not considered part of a pre-existing diagnosis or syndrome; or
- Is considered clinically significant by the Investigator

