9.2. Study Visits

Study procedures are listed for each visit in the following sections and summarized in the Schedule of Assessments ([Appendix A](#)). Further details regarding the listed safety, PK, and pharmacodynamic assessments are located in Sections 11, 12, and 14, of Protocol EP-547-101, Amendment 2.0, respectively.

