### 3.5 Handling of Missing Data

For the classification of Treatment emergent adverse event (TEAE) and Concomitant medication, the following will be applied in the following order:

- a. If all dates/times (start and stop) missing, the event/medication will automatically be classified as a TEAE/Concomitant medication.
- b. For adverse events (AEs) with a missing start date/time, if the event end date/time is prior to first study drug administration, the event will not be classified as a TEAE.
- c. If only the AE start year/ medication end year is present and is the same or is after the first study drug administration year unit, the event/medication will be classified as a TEAE/Concomitant medication.
- d. If the AE start month and year/medication end month and year are present and are the same or after the first study drug administration month and year units, the event/medication will be classified as a TEAE/Concomitant medication.

For the PK analysis the following will be applied:

- a. For the concentration descriptive summaries, concentrations may be excluded if sampling time deviation is considered large to affect the profile at the discretion of the pharmacokineticist.
- b. Concentrations (plasma and skin) that are below limit of quantification (BLQ which is 10 ng/mL undiluted) prior to the first quantifiable value will be set equal to zero. Post dose BLQ concentrations will be set to missing.
- c. Where there are no results (NR), these will be set to missing.
- d. If more than 75% of values per nominal timepoint and treatment group are BLQ, then all descriptive statistics, except for nBLQ, will be denoted as not calculable (NC).
- e. For the calculation and graphical representation (semi-log and log-log plots) of geometric descriptive statistics, 0 values will be set to missing.
- f. For the purpose of calculating the non-compartmental PK parameters, plasma concentrations that are BLQ prior to the first quantifiable value will be set equal to zero. BLQ values after measurable concentrations will be set to missing.
- g. For the calculation of summary statistics of PK parameters, all NR and NC values in a data series will be set to missing.

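### In the food-effect segment, SAP 3.2 allocates even a fall in severity by its own start, so a Period 1 AE that merely eases after the Period 2 dose is also scored under the other food condition

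*SAP*

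**What the plan says.** SAP 3.2 (Key Definitions) has two start-based rules for the FE segment. For the second period: "TEAEs that start on or after the study drug administration of Period 2 will be attributed to Period 2 treatment only". For the first period, the rule covers "TEAEs that start on or after the study drug administration of Period 1 but prior to study drug administration of Period 2" and attributes those events to Period 1 treatment alone. Immediately after these rules comes: "Any change in severity will be seen as a new event and will be allocated to the treatment in the same way".

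The data will contain such changes as separate records. Protocol 11.1.4.1 instructs: "If a persistent AE becomes more severe or lessens in severity, it should be recorded as a new AE on the eCRF". That applies to the FE segment too, because Section 9.2 of the addendum states: "Further details regarding the listed safety, PK, and pharmacodynamic assessments are located in Sections 11, 12, and 14, of Protocol EP-547-101".

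For the other segments, SAP 3.2 defines TEAEs by timing, as "adverse events that occurred following the first administration of study medication". SAP 3.5 classifies partly dated AEs by their start: "If the AE start month and year/medication end month and year are present and are the same or after the first study drug administration" counts as treatment-emergent. Protocol 11.1.1 uses a different idea: "Medical conditions present at baseline that worsen in severity or frequency after exposure to study drug are considered treatment-emergent AEs".

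SAP 13.1 restricts every AE summary to TEAEs and shows both participants and events. SAP 3.7.3 presents FE safety tables by fed and fasted, with an Overall column for AEs.

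**The concern.** A record created because an AE has improved is not evidence that something new emerged after the later dose. The FE rule does not separate the two directions, so an improving AE is charged to the condition that happened to be given second, while an AE that fails to improve is not. Recovery is scored worse than persistence.

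The affected displays are the FE TEAE tables in SAP Section 18: overall, by system organ class and preferred term, by maximum severity and, where the AE qualifies, the serious, drug-related and withdrawal tables. With 12 participants, one misplaced participant is visible in the fed-versus-fasted comparison. The listings show the split records but do not correct the tables.

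**Working it through.** The documents give no figure on this point, so there is none to reproduce. The check applies the rules to an example and then sizes one case.

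**Inputs**
- Allocation rules and the severity-change sentence: SAP 3.2.
- New record on lessening: Protocol 11.1.4.1.
- 12 subjects, two-period crossover: Addendum 7.1 and 7.3.
- Doses at least 10 days apart: Addendum 7.1.
- Three-point severity scale (mild, moderate, severe): Protocol 11.1.2.

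**Step 1. Apply the rule.** Assume the Period 1 dose on Day 1 and the Period 2 dose 10 days later, on Day 11. A moderate AE starts on Day 8 and is ongoing at the second dose.

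| Course after the Period 2 dose | Records | Attributed to |
|---|---|---|
| Stays moderate | moderate, start Day 8 | Period 1 only |
| Eases to mild on Day 12 | moderate, start Day 8; mild, start Day 12 | Period 1 and Period 2 |

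The second row is one continuous, improving AE counted under both food conditions.

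**Step 2. Size per case.** With all 12 subjects dosed in both periods, each condition's column has N = 12. A participant with no other TEAE of that preferred term in the Period 2 column adds 1/12 = 8.3 percentage points to it. Two such participants add 2/12 = 16.7 points.

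**Step 3. How long the AE must last.** At the minimum 10-day separation, an AE starting on Period 1 Day d reaches the second dose if it lasts 10 − (d − 1) = 11 − d days: 10 days for Day 1 onset, 8 for Day 3, 3 for Day 8 and 1 for Day 10. A longer separation adds the same number of days.

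**Step 4. What limits the number of cases.** A mild AE cannot step down on the three-point scale, so the AE must be at least moderate at the Period 2 dose. It must then ease rather than simply resolve. The documents give no AE rates from which a frequency could be computed.

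**Step 5. Direction.** In Sequence 1 the second condition is fed; in Sequence 2 it is fasted. With 1:1 sequences the error has no fixed direction.

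**Step 6. Other segments, by inference.** Take an AE that begins after consent, is moderate on Day −1 and eases to mild after the first dose. The original record is not a TEAE. Protocol 11.1.4.1 opens a second record, and its start satisfies the timing-only definition. One such participant would add 1/6 = 16.7 points in a six-subject active group. In the pooled EP547 columns the addition would be 1/(3 × 6) = 1/18 = 5.6 points in MAD-HS and, with five dose levels, 1/(5 × 6) = 1/30 = 3.3 points in SAD-HS. Findings before consent are medical history (Protocol 11.1.4) and do not enter.

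**The case against.** The strongest defence is that the SAP follows the protocol, which expressly records lessening as a new AE, and that its conventions lean towards inclusion: wholly undated FE events go to both periods, and same-month starts count as treatment-emergent. Over-inclusion can be a deliberate choice for descriptive safety tables. This explains why the extra record exists, but not why it should move to the other treatment. Over-inclusion is also not conservative when columns are compared, since the extra participant may fall under either condition.

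The defence is right on weight. Cases should be rare, the FE objective is pharmacokinetic, both conditions are EP547 75 mg, and the number of participants in the Overall column does not change.

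Three stronger readings may tempt a reader and are not supported:
- **That the allocation rule causes the double event count in Overall.** The two events come from record splitting (Protocol 11.1.4.1 and the new-event wording in SAP 3.2). They would arise equally if the AE eased wholly within Period 1, and re-allocating the second record does not remove them.
- **That the SAP states the same rule outside FE.** It does not. A continuous AE that began before dosing can be read as not having occurred after it, and SAP 3.5 concerns only missing or partial dates.
- **That Protocol 11.1.1 makes worsening the sole route to a TEAE.** It says that worsening qualifies; it does not say that nothing else does.

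**Conclusion.** The point stands for the FE segment on the plain text: the SAP attributes the improvement of a Period 1 AE to the Period 2 food condition, and no other provision corrects it. The size is 8.3 percentage points per affected participant in the wrong column, assuming all 12 subjects are dosed under both conditions and the participant has no other TEAE of that preferred term there. The total effect cannot be estimated, is likely to be small, and touches no formal test or stopping rule. It is a modest correction that should be made because it is simple and the present result is illogical.

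For the other segments the conclusion is conditional. The protocol's recording rule and the timing-only definition together could make an easing pre-dose AE treatment-emergent. The SAP should settle this, but it does not explicitly prescribe that result. The annotated CRF cited in SAP Section 21 was not available, so whether it links such records could not be checked. Linkage alone would not override the FE sentence.

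**What to change.** In SAP 3.2, FE segment, replace the severity-change sentence with: *An increase in severity over the immediately preceding record of the same ongoing event is a new event and is allocated by its own start; a decrease in severity remains attributed to the treatment to which the preceding record was allocated.*

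The comparison should be with the preceding record, not with severity at dosing. An AE that is moderate at the Period 2 dose, falls to mild and returns to moderate would then have its re-worsening placed under Period 2. A test against severity at dosing would miss it.

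For the other segments, add the same increase/decrease rule to the general TEAE definition, and state that a decrease in an AE that began before the first dose is not treatment-emergent. For SAD-HS and MAD-HS, the addendum reports conduct complete, the Sponsor is unblinded (Protocol 9.3.2) and an unblinded interim is planned (SAP 16.1). There, record the rule as a documented change (SAP Section 15 currently lists none) and show any difference from the interim tables.

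Keep all records in the listings and leave Protocol 11.1.4.1 unchanged. Event counts will still include split records, and the change should not be presented as correcting the Overall event count.

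The cost is two or three SAP sentences and a short derivation matching contiguous records of the same event within participant. No protocol amendment is needed.

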### 3.3 Inferential Analyses

Descriptive statistics will be used to summarize the safety and PK data. No formal hypothesis testing is planned. To further explore on the plasma PK data, dose proportionality will be assessed for SAD-HS and MAD-HS segments.

- Dose Proportionality

- SAD-HS

Dose proportionality will be assessed for  $C_{max}$ ,  $AUC_t$  and  $AUC_{0-inf}$  using the power model. An assessment of dose proportionality will not be based strictly on statistical rules criteria but rather, several factors will be considered when assessing dose proportionality, such as results derived from a Power Model (e.g., the slope estimate, and the width of the 90% confidence intervals [CIs]), graphical evaluation, and descriptive statistics by dose level.

Details are as follows:

- Power Model: The power model will be used to estimate the slope parameter and the 90% CIs for the slope. The general form of the power model is described as:

$$\ln(\text{PK Parameter}) = \beta_0 + \beta_1 \ln(\text{Dose}) + \varepsilon$$

This approach is usually referred to as a power model because after exponentiation:

$$\text{PK Parameter} = \alpha \text{Dose}^{\beta_1}$$

where  $\alpha$  only depends on  $\beta_0$  and  $\varepsilon$  and represents the y-intercept of the line and  $\beta_1$  represents the slope of the line.

Linear relationships between the log-transformed PK parameter and the log of the dose will be tested to obtain an estimate of the slope parameter ( $\beta_1$ ) and 90% confidence interval (CI) for the slope. Dose proportionality can generally be concluded if the 90% CI around the slope estimate (i.e.,  $\beta_1$ ) includes the value of 1.

- MAD-HS

- Similar model as explained above will be used to assess dose proportionality for the parameters  $C_{max}$ ,  $AUC_t$ ,  $AUC_{0-inf}$  and  $AUC_{\tau}$  calculated on Day 1 and Day 7 separately.

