5. BACKGROUND AND RATIONALE

Protocol EP-547-101 is a first-in-human, Phase 1, randomized, single and multiple ascending dose (SAD and MAD) study with EP547 in healthy subjects and subjects with cholestatic or uremic pruritus. Each population includes a SAD or single dose (SD) segment followed by a MAD segment for a total of 6 segments (SAD-HS and MAD-HS in healthy subjects [HS]; SD-CP and MAD-CP in subjects with cholestatic pruritus [CP]; and SD-UP and MAD-UP in subjects with uremic pruritus [UP]).

To date, clinical conduct for SAD-HS and MAD-HS is complete; evaluations in subjects with cholestatic or uremic pruritus are ongoing. EP547 has been tested in 48 healthy subjects with 18 treated in the multiple dose regimen. Dosing levels evaluated in healthy subjects included 25 mg to 675 mg single doses and 25, 75, and 225 mg multiple dose regimens. All doses tested to date were well tolerated with no safety signals identified.

For this addendum, a food effect segment in healthy subjects (FE-HS) at a single site will be evaluated. Data from this substudy will provide data to inform appropriate dosing instructions for future studies.

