### 3.7 Treatment Groups/Treatment Sequence

#### 3.7.1 Baseline Characteristic, Demography, Safety and PD outputs

For listings, all segment data will be presented together in one listing as per segment and dose level (available) with the following treatment group labels:

- Group 1: SAD HS/ EP547 25 mg
- Group 2: SAD HS/ EP547 75 mg
- Group 3: SAD HS/ EP547 225 mg
- Group 4: SAD HS/ EP547 450 mg
- Group 5: SAD HS/ EP547 TBD mg
- Group 6: MAD HS/ EP547 25 mg QD
- Group 7: MAD HS/ EP547 75 mg QD
- Group 8: MAD HS/ EP547 TBD mg QD
- Group 9: SD CP/ EP547 TBD mg
- Group 10: SD UP/ EP547 TBD mg
- Group 11: MAD CP/ EP547 TBD mg QD
- Group 12: MAD CP/ EP547 TBD mg QD (optional)
- Group 13: MAD UP/ EP547 TBD mg QD
- Group 14: MAD UP/ EP547 TBD mg QD (optional)

For summary, separate tables will be provided for each segment (SAD-HS, MAD-HS, SD-CP/SD-UP, MAD-CP/MAD-UP) with the following treatment group labels:

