### 10.4.3 Inferential Analyses

For SAD-HS and MAD-HS, the following endpoints will be analyzed as described in section 3.3:

- Dose proportionality:
  - $C_{\text{trough}}$  (Only Day 7 value to be used to assess DP for MAD )
  - $C_{\text{max}}$
  - $AUC_{0-t}$
  - $AUC_{0-\text{inf}}$
  - $AUC_{0-\tau}$  (as appropriate, MAD only)

Dose proportionality will be assessed graphically ( $C_{\text{max}}$ ,  $AUC_{0-t}$  and  $AUC_{0-\text{inf}}$  versus dose) on log scale for both axes. PK parameters derived from Day 1 (SAD & MAD) and Day 7 (MAD) will be subjected to dose proportionality assessment for entire dose range studied for EP-547-101. From each model, the slope of the regression line  $\beta$  will be presented along with the 90% CI of the slope. The regression line formulae along with correlation coefficient ( $r^2$ ) will be presented in the plot.

Sample SAS Code for dose-proportionality analysis using power model. Programmers will need to modify as appropriate to the study:

```
proc mixed;  
  by PKParameter;  
  model lnPKParameter = lnDose / cl alpha=0.1 solution ddfm=kr;  
run;
```

For FE-HS, the following endpoints will be analyzed as described in section 3.3:

- Food Effect analysis:

- o  $C_{\max}$
- o  $AUC_{0-t}$
- o  $AUC_{0-\infty}$
- o  $T_{\max}$

[REDACTED]

- [REDACTED]
- [REDACTED]
- [REDACTED]
- [REDACTED]
- [REDACTED]
- [REDACTED]
- [REDACTED]
- [REDACTED]

[REDACTED]

- [REDACTED]
- [REDACTED]
- [REDACTED]

**11.1** [REDACTED]

[REDACTED]

**11.2** [REDACTED]

[REDACTED]

**11.3** [REDACTED]

[REDACTED]

- [REDACTED]
- [REDACTED]
- [REDACTED]
- [REDACTED]
- [REDACTED]
- [REDACTED]
- [REDACTED]
- [REDACTED]
- [REDACTED]

[REDACTED]

[REDACTED]

[REDACTED]

[REDACTED]

[REDACTED]

[REDACTED]

[REDACTED]

[REDACTED]

[REDACTED]

[REDACTED]

[REDACTED]

[REDACTED]

[REDACTED]

[REDACTED]

[REDACTED]

[REDACTED]

[REDACTED]

[REDACTED]

[REDACTED]

[REDACTED]

[REDACTED]

**11.7** [REDACTED]

[REDACTED]

[REDACTED]

[REDACTED]

[REDACTED]

[REDACTED]

[REDACTED]

[REDACTED]

[REDACTED]

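### The SAP's only conclusion rule for dose proportionality is that the slope's 90% CI includes 1, with no width limit and no inconclusive outcome, in both SAD-HS and MAD-HS

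*SAP*

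**What the plan says.** SAP 3.3 regresses the log PK parameter on log dose and gives the slope with a 90% CI. It frames the work as exploratory: "No formal hypothesis testing is planned", and the assessment "will not be based strictly on statistical rules criteria but rather, several factors will be considered". Those factors include "the slope estimate, and the width of the 90% confidence intervals", together with graphs and descriptive statistics by dose.

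It then gives one sentence that turns a result into a conclusion: "Dose proportionality can generally be concluded if the 90% CI around the slope estimate" includes 1. For MAD-HS it says "Similar model as explained above will be used to assess dose proportionality for the parameters" on Day 1 and Day 7 separately, and gives no other criterion. SAP 10.4.3 refers both segments back to 3.3 and says the slope "will be presented along with the 90% CI of the slope". Protocol 15.5 leaves the details to the SAP. None of these sections sets a maximum CI width, a reference region for the slope or an inconclusive category.

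**The concern.** A 90% CI that includes 1 shows only that the data do not contradict proportionality at that level. If the true slope is 1, the criterion is met 90% of the time at any precision. If the true slope is not 1, the chance of meeting it rises as the CI widens. The rule therefore favours imprecise data, which is the wrong direction for a positive claim.

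Listing CI width as a factor does not repair this, because the SAP never says how width changes the conclusion. A wide CI that contains 1 still satisfies the only stated criterion. The report could then call exposure dose proportional when the data do not exclude a material departure. SAP section 1 allows the planned analyses to be used in study reports, regulatory submissions and manuscripts, so the statement may be read outside this study.

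**Working it through.** **No figure to reproduce.** The SAP gives no precision or sample size calculation for this analysis, so the check is of the criterion's operating characteristics.

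**Inputs**
- 6 active subjects per healthy-subject dose level (Protocol 7.1.1).
- Protocol Addendum 1.0, section 5: "EP547 has been tested in 48 healthy subjects with 18 treated in the multiple dose regimen". Single doses ran from 25 to 675 mg; multiple doses were 25, 75 and 225 mg.
- SAP 3.7.1 lists 25, 75 and 225 mg, then "Group 4: SAD HS/ EP547 450 mg", with the fifth single dose still open. I take it as 675 mg. The counts agree: 48 − 18 = 30 = 5 × 6 single-dose, and 18 = 3 × 6 multiple-dose.
- Between-subject CV: not given. Assumed 20, 30, 40 and 60%.

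**Formulas**
- σ = √ln(1 + CV²); SE(slope) = σ/√Sxx, where Sxx is the sum of squares of log dose about its mean.
- A total departure R over a dose range r corresponds to slope = 1 ± ln R/ln r.
- Chance that the 90% CI includes 1 = P(|T| ≤ t(0.95, n−2)), with T noncentral t and noncentrality (slope − 1)√Sxx/σ.

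**Design constants**
- MAD-HS: Sxx = 6 × 2 × (ln 3)² = 14.48; n = 18; df = 16; t = 1.746; r = 225/25 = 9.
- SAD-HS: mean log dose 5.115; Sxx = 6 × (3.596 + 0.636 + 0.090 + 0.988 + 1.958) = 43.62 from unrounded terms; n = 30; df = 28; t = 1.701; r = 675/25 = 27.

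**Worked example: R = 1.5, CV 40%, MAD-HS.** σ = √ln 1.16 = 0.385. SE = 0.385/√14.48 = 0.101. Slope − 1 = ln 1.5/ln 9 = 0.185. Noncentrality = 1.82, and the chance that the CI includes 1 is 46.0%. For SAD-HS, SE = 0.058, slope − 1 = ln 1.5/ln 27 = 0.123, noncentrality = 2.11, chance 34.0%. Direct regression simulation (200,000 trials) gave 46.0% and 34.1%.

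**Chance that the criterion is met although exposure is not proportional**

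| Total departure over the segment's range | Segment (slope) | CV 20% | 30% | 40% | 60% |
|---|---|---|---|---|---|
| 39% above or 28% below | MAD-HS (1.15/0.85) | 13% | 41% | 59% | 74% |
| | SAD-HS (1.10/0.90) | 5% | 29% | 49% | 68% |
| 50% above or 33% below | MAD-HS (1.185/0.815) | 4% | 26% | 46% | 66% |
| | SAD-HS (1.123/0.877) | 1% | 15% | 34% | 58% |
| 100% above or 50% below | MAD-HS (1.315/0.685) | 0% | 1% | 9% | 33% |
| | SAD-HS (1.210/0.790) | 0% | 0% | 3% | 21% |

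**What a best-case result would exclude.** Suppose the estimated slope is exactly 1. The expected CI half-width is t × SE, and the CI for the highest-to-lowest dose-normalised exposure ratio is r^(±half-width).

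| CV | MAD-HS half-width | MAD-HS ratio CI | SAD-HS half-width | SAD-HS ratio CI |
|---|---|---|---|---|
| 30% | 0.135 | 0.74–1.34 | 0.076 | 0.78–1.28 |
| 40% | 0.177 | 0.68–1.47 | 0.099 | 0.72–1.39 |

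**The case against.** The strongest reply is that SAP 3.3 already disclaims a mechanical rule. It says no strict criterion governs, names CI width as a factor and uses permissive wording in the criticised sentence. SAP 10.4.3 shows the CI and a log-log plot, so a reader would see imprecision. On that reading the pass rates above model a rule the SAP does not fully adopt, and they are upper bounds on misreporting. They also rest on assumed CVs, and no document says that a 1.5-fold departure is material.

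Much of this stands. The defect is the absence of any stated consequence of a wide CI, not disregard of width. A two-fold departure passes only 1% (MAD-HS) and 0% (SAD-HS) of the time at CV 30%.

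The contrast between segments also depends on the metric. At a fixed slope of 0.8 and CV 30 and 40%, the CI includes 1 in 20 and 40% of cases in MAD-HS, but in 0.3 and 5% in SAD-HS. That slope, however, means exposure 36% below proportional over 9-fold (9^−0.2 = 0.64) and 48% below over 27-fold (27^−0.2 = 0.52), so the total departures are not equal.

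The reply does not remove the point. Section 3.3 contains one sentence that licenses a conclusion, and that sentence is easier to satisfy with poor data. Nothing in the SAP tells the report's author to withhold the conclusion.

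**Conclusion.** The concern holds and should be corrected, although it does not threaten the trial's primary objective. Both segments are affected. At equal total departure, MAD-HS is moderately worse because it has 18 active subjects over a 9-fold range, against 30 over 27-fold. MAD-HS is not read alone, since SAD-HS spans all its doses. The practical problem lies with departures of about 1.5-fold or less at CVs of roughly 30% and above; larger departures become a concern only at higher CVs. The analysis is exploratory and no document ties a dose decision to the result.

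The sizes depend on the assumed CVs, 6 evaluable active subjects per dose, 675 mg as the fifth single dose, and log-normal errors with constant variance. The direction of the fault depends on none of the assumed CVs.

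**What to change.** Replace the sentence in SAP 3.3 that concludes proportionality when the CI includes 1. Suggested content, for both segments:

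- Report the slope with its 90% CI.
- Report the implied highest-to-lowest dose-normalised exposure ratio, r^(slope − 1), with its 90% CI (r = 27 in SAD-HS, 9 in MAD-HS).
- State that a CI which includes 1 but also includes material departures is inconclusive.
- No fixed acceptance region is required. If the sponsor wants a yes/no conclusion, it should prespecify and justify the limits.

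The cost is wording: the ratio is a transformation of output already planned, and no new data are needed. The downside is that inconclusive will be reported more often. As an illustration, take a true slope of 1 and treat 1.5-fold as material (an assumption). Of the results now read as proportional, the share that would become inconclusive at CV 20, 30, 40 and 60% is about 4, 47, 84 and 99% in MAD-HS and 0, 22, 64 and 98% in SAD-HS. That reflects what these group sizes can support.

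SAP 16.1 plans an unblinded interim analysis of these two segments, and the dose-proportionality tables are marked for it. If the wording changes after those results have been seen, the report should say so.
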